11.0 ENDPOINT DEFINITIONS/MEASUREMENT OF EFFECT

11.1 Assessment of Response

Lymphoma response/progression will be evaluated using 2014 Lugano Classification (see Appendix B). [38]

Disease assessment will be performed by PET-CT. For patients in CR, diagnostic quality CT is acceptable at the end of consolidation and during active Follow-up. Assessment with PET-CT is required to confirm CR. Patients with bone marrow involvement at baseline must have a bone marrow biopsy performed to confirm CR (if applicable). After CR, additional bone marrow biopsy is only required if clinically indicated. Additional necessary restaging studies including dedicated CT scans or MRI, are permitted at the investigator's discretion. PET-CT and CT results will be read by a radiologist at each study site and investigator response assessment will be performed.

For patients with progression of disease on imaging, it is strongly recommended that a confirmatory biopsy be obtained whenever possible.

11.2 Primary Endpoint(s)

Unacceptable Toxicity: defined as any of the following events occurring during the first 2 cycles of treatment that is at least possibly related to study treatment:

- Any Grade 3 or higher non-hematologic toxicity that does not resolve to Grade 1 or better within 7 days with the exception of:
 - Grade 3 asymptomatic laboratory abnormalities, including lipase or amylase, that are not clinically relevant, not requiring hospitalization or delay of treatment
 - Grade 4 isolated electrolyte abnormalities that are not clinically significant including, but not limited to, hypo-or hyperglycemia, hypo-or hypernatremia, hypo-or hyperkalemia, hypo-or hypermagnesemia, or hypo-or hypophosphatemia, that resolve, with or without intervention, to Grade 2 in less than 72 hours
 - Grade 3 nausea, vomiting, or fatigue controlled with supportive measures (and does not require hospitalization, TPN, or tube feeding)
 - Grade 3 infusion reaction that resolves with appropriate management to Grade 1 or better within 24 hours
 - Alopecia of any grade
- Any Grade 3 or 4 thrombocytopenia associated with clinically significant bleeding.
- Any Grade 4 neutropenia (despite the use of growth factor) or grade 4 thrombocytopenia (without clinically significant bleeding) that lasts > 21 days.
- Any Grade 4 anemia unexplained by underlying disease.
- Any treatment-related toxicity that delays cycle 2 treatment for >2 weeks.
- Any Grade 5 toxicity.

Complete response (CR) rate: defined as the proportion of response-evaluable participants (see Section 12.2) that achieve a CR after 2 cycles of PolaR-ICE therapy.

11.3 Secondary Endpoint(s)

Overall response rate (ORR): defined as the proportion of response-evaluable participants (see Section 12.2) that achieve a best response of either CR or PR at the end of PolaR-ICE therapy.

Progression-Free Survival (PFS): defined as the duration of time from start of protocol treatment to time of disease relapse/progression or death due to any cause, whichever occurs earlier. For patients who are alive and have not had disease relapse/progression at the last follow-up, it is censored at the time of last follow-up. If a patient starts non-protocol anti-lymphoma therapy without disease relapse/progression, it will be censored at the start of the non-protocol anti-lymphoma therapy.

Overall Survival (OS): defined as the duration of time from start of protocol treatment to time of death due to any cause. For patients who are alive at last follow-up, it will be censored at the time of last follow-up.

CR rate among patients who were PR at ASCT: defined as the proportion of patients that achieve CR after Pola consolidation among those who were PR at ASCT.

Stem cell mobilization failure rate: defined as the portion of patients who failed to collect adequate CD34 stem cells (within 2 attempts) among those who attempt stem cell collection.

11.4 Exploratory Endpoint(s)

Exploratory endpoints include ctDNA measures and other biomarkers.

12.0 STATISTICAL CONSIDERATIONS

12.1 Study Design

This is a multicenter, single-arm Phase 2 study evaluating PolaR-ICE as initial salvage therapy before ASCT for relapsed and refractory DLBCL. PolaR-ICE salvage therapy will be given in 21-day cycles. Patients will first receive 2 cycles of PolaR-ICE; patients in CR after 2 cycles may proceed to ASCT or may receive a 3rd salvage cycle of PolaR-ICE at the treating physician's discretion. Patients in PR after 2 cycles will receive a 3rd salvage cycle of PolaR-ICE. Patients in SD after 2 cycles may receive a 3rd salvage cycle of PolaR-ICE at the treating physician's discretion. A patient may proceed to ASCT if patient is CR/PR after 3 cycles, otherwise the patient will go off protocol. After ASCT, patients who received 2 salvage cycles of PolaR-ICE will receive 4 cycles of single-agent Pola (21-day cycles) as consolidation therapy, while patients who received 3 salvage cycles of PolaR-ICE will receive 3 consolidation cycles of single-agent Pola.

The primary endpoint is complete response (CR) rate after 2 cycles of PolaR-ICE salvage therapy. Secondary endpoints include toxicities of PolaR-ICE salvage therapy, toxicities of single-agent Pola consolidation therapy, overall response rate to PolaR-ICE, the rate of stem cell mobilization and collection failure in patients who attempt stem cell collection, progression free survival, overall survival, and CR rate after Pola consolidation among patients who were PR at ASCT.

The first 5-16 patients will be monitored as part of the Safety Lead-in portion as described below in Section 12.1.1 to confirm the tolerable dose of PolaR-ICE. Once the tolerable dose level of PolaR-ICE is confirmed, the study will go into the Phase 2 portion with a 2-stage design and a total sample size of 40 patients for the Phase 2 response evaluation.

12.1.1 Safety Lead-in

Prior to formally initiating the Phase 2 response assessment, a patient safety lead-in portion will be conducted to ensure there are no unexpected toxicities with PolaR-ICE salvage therapy. The decision to open to Phase 2 will primarily be based on the number of safety lead-in patients experiencing unacceptable toxicities during the first 2 cycles of PolaR-ICE salvage, but will also take into consideration other data available at the time of decision making, including toxicities observed in cycle 3, the ability to

proceed to transplant after PolaR-ICE and delays due to study treatment-related toxicity between PolaR-ICE and transplant. The unacceptability toxicities are defined in Section 11.2. Patients evaluable for unacceptable toxicities during the Safety Lead-in are defined in Section 12.2.

During the safety lead-in portion of the study, a design that is slightly modified from the IQ rolling 6 design will be used.[7] In this design, up to 8 evaluable patients may be treated at each dose level, and the highest dose level with <33% evaluable patients having unacceptable toxicities will be considered tolerable with respect to unacceptable toxicities. Given the expected safety profile of PolaR-ICE, we adopt this design which may allow up to 6 patients at risk at any time instead of some other designs which allow up to 3 at risk. The rules of the proposed design are outlined below.

- 1) When there is no patient with unacceptable toxicities, accrual can continue for up to 8 patients with up to 6 patients at risk (i.e., under unacceptable toxicity observation) at the same time.
- 2) If there is no DLT in 5+ evaluable patients with no others at risk, (i.e., 0/5, 0/6, 0/7, or 0/8), the current dose level will be considered tolerable.
- 3) After 1 patient with unacceptable toxicity is reported, accrual can continue to up to 6 patients (i.e. <6 at risk); to accrue the 7th or the 8th patient, there must be ≤3 patients at-risk.
- 4) If there is 1 patient with unacceptable toxicity in 6-8 evaluable patients with no others at risk (i.e., 1/6, 1/7, or 1/8), the current dose level will be considered tolerable.
- 5) If there are 2 patients with unacceptable toxicities when ≤6 patients are treated, the current dose level will be considered intolerable (and dose de-escalated if at dose level 1).
- 6) If there are 2 patients with unacceptable toxicities when 7 or 8 patients are treated, accrual to this dose level will be on hold if there are still any patients at risk. If the rate of unacceptable toxicity is ≥33% (i.e., 2 out of ≤6, 3/7, or 3/8 evaluable), the current dose level will be considered intolerable (and the dose de-escalated if at dose level 1); if the rate of unacceptable toxicity is <33% (i.e., 2/7 or 2/8 evaluable), the dose level will be considered tolerable.
- 7) Any time 3+ patients with unacceptable toxicities occur, the current dose level will be considered intolerable (and dose de-escalated if at dose level 1).

12.1.2 Phase 2 design

The Phase 2 portion of the study adopts a two-stage design. Patients who were enrolled during the safety lead-in portion at the final dose level deemed tolerable for Phase 2 will also be included in the Phase 2 response evaluation if they are evaluable for response.

At the first stage, 20 patients will be enrolled. If <8 complete responses are seen, the accrual will be terminated. If at least 8 patients achieve a complete response, the trial will continue to the second stage. At the second stage, 20 additional patients will be entered. At the end of stage 2, if 21 or more patients out of the total 40 patients experience a complete response, the combination will be considered worthy of further study. If <21 patients experience a complete response then no further investigation of the combination is warranted.

The 2-stage design aims to differentiate between the null hypothesis (disappointing rate) of 40% CR rate and an alternative hypothesis (promising rate) of 60% CR rate. The null hypothesis of 40% CR rate is based on a large randomized study comparing R-ICE with R-DHAP (rituximab, dexamethasone, cytarabine, cisplatin) as salvage regimen followed by ASCT for relapsed/refractory DLBCL.[8] Similar complete

response rates were observed after 3 cycles of R-ICE (37%, n=197) vs. 3 cycles R-DHAP (40%, n=191). Therefore, we would consider a 40% CR rate a discouraging rate and 60% a promising CR rate for this regimen to merit further study. The design has a 1-sided type I error of 7.3% and a power of 87%. The expected sample size under the null hypothesis is 31.7, and the design has a 42% chance of early termination after Stage I if the true CR rate is 40%.

12.2 Evaluable Participants and Participant Replacement

- Evaluable for toxicity: Patients who receive at least one dose of protocol therapy are evaluable for toxicity.
- Evaluable for unacceptable toxicity during Safety Lead-in: Patients evaluable for unacceptable toxicity (defined in Section 11.2) are:
 - 1) Those who receive the full dose of Pola, the full doses of rituximab and carboplatin, and at least 67% of the doses of etoposide and ifosfamide during the first 2 cycles of Salvage, OR
 - 2) Those who experience any unacceptable toxicity during the first 2 cycles of Salvage regardless of actual dose of protocol therapy received.

During safety lead-in, patients who are not evaluable for unacceptable toxicities will be replaced.

• Evaluable for response during Phase 2:

Evaluable patients are defined as eligible participants who have received at least one cycle of PolaR-ICE salvage therapy and have at least one disease evaluation post-baseline.

Patients will be evaluable and be considered non-CR in the primary response evaluation if they discontinued study therapy prior to having a response assessment after 2 cycles of PolaR-ICE because of progressive disease or unacceptable toxicity (rather than due to withdrawal of consent or investigator decision). If a patient discontinues study treatment prior to the first response assessment after 2 cycles of PolaR-ICE due to progressive disease, the treating physician is encouraged to obtain imaging to confirm progression.

During Phase 2 enrollment, participants who are not evaluable for response will be replaced and excluded from Phase 2 efficacy analyses, but will be included in the general toxicity analyses if they receive any protocol treatment.

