6.4 Carboplatin

According to the package insert for carboplatin, carboplatin can cause:

- Hematologic Toxicity: Bone marrow suppression is the dose-limiting toxicity of carboplatin. Thrombocytopenia with platelet counts below 50,000/mm³ occurs in 25% of the patients; neutropenia with granulocyte counts below 1000/mm³ occurs in 16% of the patients; leukopenia with WBC counts below 2000/mm³ occurs in 15% of the patients. The nadir usually occurs about day 21 in patients receiving single-agent therapy. By day 28, 90% of patients have platelet counts above 100,000/mm³; 74% have neutrophil counts above 2000/mm³; 67% have leukocyte counts above 4000/mm³.
 - Anemia with hemoglobin less than 11 g/dL has been observed in 71% of the patients who started therapy with a baseline above that value. The incidence of anemia increases with increasing exposure to carboplatin. Transfusions have been administered to 26% of the patients treated with carboplatin.
 - Bone marrow depression may be more severe when carboplatin is combined with other bone marrow suppressing drugs or with radiotherapy.
- Gastrointestinal Toxicity: Vomiting occurs in 65% of the patients and in about one-third of these patients it is severe. Nausea alone occurs in an additional 10 to 15% of patients. Both nausea and vomiting usually cease within 24 hours of treatment and are often responsive to antiemetic measures. Emesis was increased when

- carboplatin was used in combination with other emetogenic compounds. Other gastrointestinal effects observed frequently were pain, in 17% of the patients; diarrhea, in 6%; and constipation, also in 6%.
- *Neurologic Toxicity:* Peripheral neuropathies have been observed in 4% of the patients receiving carboplatin with mild paresthesias occurring most frequently.
 - Clinical ototoxicity and other sensory abnormalities such as visual disturbances and change in taste have been reported in only 1% of the patients. Central nervous system symptoms have been reported in 5% of the patients and appear to be most often related to the use of antiemetics.
- Nephrotoxicity: Development of abnormal renal function test results is uncommon, despite the fact that
 carboplatin, unlike cisplatin, has usually been administered without high-volume fluid hydration and/or
 forced diuresis. The incidences of abnormal renal function tests reported are 6% for serum creatinine and
 14% for blood urea nitrogen (10% and 22%, respectively, in pretreated ovarian cancer patients). Most of

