17.5 Participant Withdrawal

Participants may withdraw from the study at any time and for any reason without prejudice. The withdrawal must be documented per institutional policies. The COH DCC should be promptly notified of the change in participant status.

Participant withdrawal may consist of any of the following with regard to study procedures and data collection:

- Withdrawal from study treatment, but agreement to continue with active study procedures and chart review and survival follow-up.
- Withdrawal from study treatment and all active procedures, but agreement for chart review and survival follow-up.
- Withdrawal from study treatment, all active procedures, and any future data collection.

Participants who agreed to the collection of research blood samples may withdraw consent to use their specimens, if they are not yet processed as detailed in the consent form. Once the PI and site PI is notified of this withdrawal of informed consent, the research specimens will not be used in any research. At that time, any of the existing specimens will be destroyed.

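### Lead-in evaluability rests on doses received, with no requirement to observe to the end of cycle 2, so a patient who leaves observation after cycle 2 dosing counts as a complete non-event

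*Combined protocol and SAP*

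**What the plan says.** Section 11.2 sets the window for the lead-in endpoint: "defined as any of the following events occurring during the first 2 cycles of treatment that is at least possibly related to study treatment". Section 5.2 gives 21-day cycles, so the window is 42 days.

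Section 12.2 offers two routes to being evaluable for this endpoint in the lead-in. The first is by dose: "Those who receive the full dose of Pola, the full doses of rituximab and carboplatin, and at least 67% of the doses of etoposide". The same share is required of ifosfamide, all counted over the two salvage cycles. The second is by event: "Those who experience any unacceptable toxicity during the first 2 cycles of Salvage regardless of actual dose of protocol therapy received". Neither mentions length of observation. The section adds: "During safety lead-in, patients who are not evaluable for unacceptable toxicities will be replaced". A patient who meets the dose route is evaluable, so is not replaced.

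Section 12.1.1 turns the evaluable count into a decision. 0/5 to 0/8, 1/6 to 1/8, 2/7 and 2/8 are tolerable; 2 out of 6 or fewer, 3/7 and 3/8 are not. The rules for zero or one event require that nobody else is still at risk, and with two events accrual is held while anyone is. At risk is explained in the phrase "up to 6 patients at risk (i.e., under unacceptable toxicity observation) at the same time".

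Section 17.5 allows for a patient who leaves observation entirely: "Withdrawal from study treatment, all active procedures, and any future data collection".

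**The concern.** The endpoint is defined over a period of time, but the denominator is defined by doses given early in each cycle. Once the cycle 2 doses are in, an event-free patient is evaluable whatever is seen afterwards. If observation then stops, the patient is no longer at risk in the Section 12.1.1 sense, so the decision need not wait. The patient is evaluable, so is not replaced, and has no recorded event, so counts as tolerating the regimen. Unseen toxicity can only be missed, so the error runs in one direction.

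The lead-in decides with 5 to 8 patients per dose level whether Phase 2 opens and at which Pola dose. With counts this small, one patient can decide the outcome.

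**Working it through.** **1. The plan's boundaries reproduce.** 2/6 = 33.3%, 3/7 = 42.9% and 3/8 = 37.5% are at or above 33%. 2/7 = 28.6% and 2/8 = 25.0% are below it.

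**2. When the dose condition is met (Table 5.3).** Pola and rituximab are given on Day 1, carboplatin on Day 2, etoposide on Days 1-3, and ifosfamide on Day 2 (inpatient) or Days 1-3 (outpatient). At the end of cycle 2 Day 2:
- Pola, rituximab and carboplatin: complete.
- Etoposide: 5 of 6 doses = 83%, above 67%.
- Ifosfamide: 100% inpatient, or 5 of 6 = 83% outpatient.

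This is study Day 21 + 2 = 23, leaving 42 − 23 = 19 days (19/42 = 45% of the window). If 67% is applied per cycle, etoposide on cycle 2 Day 2 is 2/3 = 66.7%, just short, and the condition is met on Day 3. The conclusion does not change.

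**3. Effect on the count** of one event-free patient who leaves observation after that point:

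| As written | If that patient is not evaluable | Effect |
|---|---|---|
| 0/5, tolerable | 0/4, no decision yet | decision came early |
| 1/6, tolerable | 1/5, no decision yet | decision came early |
| 2/7, tolerable | 2/6, intolerable | verdict reverses |
| 2/8, tolerable | 2/7, tolerable | none |

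Only 2/7 versus 2/6 reverses through the denominator alone. That takes the sixth rule of Section 12.1.1 as applied to the six remaining patients; if a replacement were enrolled first, the result would depend on that patient. Separately, if the lost patient had a late event, a true 2/6, 3/7 or 3/8 would be recorded as 1/6, 2/7 or 2/8.

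**4. Effect on the chance of declaring the dose tolerable.** Assumptions, none from the documents: true rate 33%, constant hazard over 42 days, one patient lost at Day 23.
- Event-free to Day 23: 0.67^(23/42) = 0.803. Recorded event probability for the lost patient: 1 − 0.803 = 0.197.
- Clearing at 0/5, all fully observed: 0.67^5 = 13.5%. With one lost: 0.67^4 × 0.803 = 0.2015 × 0.803 = 16.2%.
- Among the other 7 patients, P(≤2) = 0.578 and P(≤1) = 0.270.
- P(≤2 of 8), all fully observed: 0.67 × 0.578 + 0.33 × 0.270 = 47.6%.
- With one lost: 0.803 × 0.578 + 0.197 × 0.270 = 51.8%.
- If the loss is at Day 35 instead: 0.67^(35/42) = 0.716, giving 0.716 × 0.578 + 0.284 × 0.270 = 49.1%.

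**5. Sensitivity to timing.** Suppose instead that 25% to 45% of events fall after cycle 2 Day 2, again with one patient lost:

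| Cohort and limit | True 33%: full observation → one lost | True 40%: full observation → one lost |
|---|---|---|
| 6, ≤1 event | 35.8% → 38.5-40.7% | 23.3% → 25.9-28.0% |
| 7, ≤2 events | 57.8% → 60.5-62.7% | 42.0% → 45.1-47.6% |
| 8, ≤2 events | 47.6% → 50.2-52.2% | 31.5% → 34.2-36.2% |

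**6. A second route to incomplete observation.** Section 14.5 suspends routine adverse event collection between the End of Salvage visit and the start of consolidation for patients going to transplant. Section 10 only requires that visit within 30 days of the last dose. After two cycles the last dose is on study Day 24, so the visit may fall anywhere up to Day 54, including before Day 42. Routine collection can therefore stop inside the window for a patient who is not lost at all.

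**The case against.** **Most patients stay under observation.** Section 10 schedules a PET-CT at cycle 2 Day 15 (±7 days), then cycle 3 Day 1 or an End of Salvage visit with adverse event review and blood counts. Full withdrawal or true loss within 19 days of dosing should be uncommon among patients heading for transplant. This stands and limits the frequency. But none of these contacts is a condition of evaluability.

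**The decision is not mechanical.** Section 12.1.1 also weighs cycle 3 toxicity, ability to reach transplant and delays, and the Protocol Management Team and DSMC review safety. A fully dosed patient who disappeared would probably be noticed. That softens the effect, but discretion cannot supply data that were never collected.

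**Counting the patient as a non-event may be correct.** Under the assumptions in step 4, a patient event-free at Day 23 has a 1 − 0.67/0.803 = 16.6% chance of a later event in the window, so the count would usually be right. Excluding the patient also discards 23 event-free days and pushes the observed rate up. This is fair, and it is why a reader should not infer that a dose cleared at 2/7 is in truth intolerable.

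**Wider readings that the documents do not support:**
- *Patients who die or start other lymphoma treatment are also unobserved.* A death is observed, and an at least possibly related Grade 5 toxicity is an event under Section 11.2. Section 5.11 puts all who end protocol therapy into follow-up with a 30-day safety contact. Table 14.6 requires serious events to be reported for 30 days after cessation even when new anticancer therapy starts; from Day 23 that reaches Day 53.
- *The unobserved days contain the carboplatin nadir.* Section 6.4 says "The nadir usually occurs about day 21 in patients receiving single-agent therapy". Cycle 2 carboplatin is given on study Day 23, so that nadir falls near Day 43 or 44, outside the window.
- *Larger effects.* Two lost patients among 8 would give 56.0%, but that is 25% of the cohort, while Section 12.3 allows up to 10% inevaluable. Clearing at 0/5 with 20.2% probability requires all toxicity to fall after Day 23, although cycle 1 gives the same drugs.

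**Conclusion.** The point holds in a limited form. The evaluability rule as written counts a patient who leaves all observation after cycle 2 dosing as a complete non-event, and no other provision removes or replaces that patient. The bias is toward declaring the dose tolerable.

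The size is modest: about 2 to 6 percentage points per lost patient across the cases in steps 4 and 5. This rests on one patient being lost, true rates of 33% to 40%, and assumed event timing. Day 23 is essentially the earliest possible loss, so the constant-hazard figures are near the upper end for one patient. The documents give neither a loss rate after dosing nor the timing of toxicity. The point does not discredit the lead-in design. It is worth correcting because the cohort is very small, the direction of error is known, and the remedy is one clause.

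**What to change.** 1. In Section 12.2, add to the dose criterion: *and were observed for unacceptable toxicity through the end of cycle 2 (Day 21 of cycle 2, or the start of cycle 3)*.
2. State that an event-free patient whose observation ends earlier is replaced for the tolerability count, but stays in the Phase 2 response evaluation if response-evaluable.
3. In Section 14.5, continue adverse event collection for lead-in patients to the end of the two-cycle window, even when the End of Salvage visit comes earlier.

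No exclusion for starting other lymphoma treatment is needed, because those patients remain observable. The clause does not settle Grade 4 cytopenia that begins after cycle 2 Day 2: it cannot have lasted more than 21 days by the end of cycle 2.

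The cost is possibly one more lead-in patient, who counts toward the 40 if treated at the final dose level and response-evaluable. The stated maximum already allows for this kind of replacement: 48 × 1.10 = 52.8, given as 53 in Section 12.3. No dose or treatment rule changes.
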